This is an open-label randomized controlled trial in which participants will be randomized to receive either nifedipine or enalapril in the postpartum period for hypertension requiring antihypertensives. Women who are pregnant or recently postpartum (within 6 weeks) with hypertension can be recruited for the study. They must also be at least 18 years old and planning to follow-up at Brigham and Women’s Hospital. They can be on no more than one antihypertensive and if they are, it must have been started in pregnancy. Women are not eligible for the study if they have any strict contraindications to nifedipine, enalapril or labetalol or a history of failed treatment with any of those agents. Their creatinine during admission must be less than 1.5. There will be 45 women recruited to each arm for a total of 90 women in the study. They will officially enter the trial once they are postpartum and their provider wants them to start or continue an antihypertensive.

All women will be enrolled by physician investigators or other physicians at Brigham and Women’s Hospital who have agreed to help consent patients for this study. All patients will give written consent and will be informed that a licensed physician investigator is available to speak with them at any time during the consent process.

Briefly describe study procedures. Include any local site restrictions, for example, “Subjects enrolled at Partners will not participate in the pharmacokinetic portion of the study.” Describe study endpoints.

Patients who participate in the study will be randomized to receive nifedipine or enalapril in the postpartum period to control hypertension. The assigned antihypertensive should be titrated to control blood pressure so that systolic blood pressure is consistently less than 150 mmHg and diastolic blood pressure is consistently less than 95 mmHg. If a patient reaches 90mg daily of nifedipine or 40mg daily of enalapril without achieving this blood pressure goal or the patient’s provider believes the assigned agent (nifedipine or enalapril) is ineffective, labetalol 200mg twice daily should be added to the regimen. Patients will follow-up in clinic in one week after discharge and six weeks for blood pressure checks and to have basic metabolic panels drawn.

At the six week visit, patients will be asked to complete a short survey. These are standard visits for postpartum patients. The study will be over once the patient has had her six-week postpartum visit.

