The patient may be contacted via telephone by study staff to verify any additional interactions with outside hospitals or medical providers (which would influence the primary outcome).

For studies involving treatment or diagnosis, provide information about standard of care at Partners (e.g., BWH, MGH) and indicate how the study procedures differ from standard care. Provide information on available alternative treatments, procedures, or methods of diagnosis.

There is no consensus on the best antihypertensive to use during the postpartum period. Currently at BWH, providers usually choose to use nifedipine, enalapril and/or labetalol to control postpartum hypertension as they are effective and safe during breastfeeding. The study procedures differ from standard care only in that it is formally randomized and not provider dependent.

There are alternative antihypertensives to use such as methyldopa or clonidine but these are rarely used at BWH.

Describe how risks to subjects are minimized, for example, by using procedures which are consistent with sound research design and which do not unnecessarily expose subjects to risk or by using procedures already being performed on the subject for diagnostic or treatment purposes.

Risks to participants are minimized because the protocol is not deviating from standard care as we are giving medications that we would normally give in the postpartum period.

Describe explicitly the methods for ensuring the safety of subjects. Provide objective criteria for removing a subject from the study, for example, objective criteria for worsening disease/lack of improvement and/or unacceptable adverse events. The inclusion of objective drop criteria is especially important in studies designed with placebo control groups.

Patients will be monitored closely in the hospital and then in the postpartum period. We will monitor their vital signs and any symptoms or side effects they may have. We would remove a patient from the study if she has an adverse reaction to any of the antihypertensives such as significant hypotension, uncontrollable hypertension or intolerance of the medication. We will follow-up with these patients one week after they are discharged from their hospitalization and at six weeks postpartum.

FORESEEABLE RISKS AND DISCOMFORTS

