Study Title: Randomized Controlled Trial Comparing Nifedipine and Enalapril in Medical Resources Used in the Postpartum Period

NCT04236258

1/3/2022

Biostatistical analysis:

The primary outcome is a composite of additional medical resources used in the postpartum period in order to control hypertension and/or the symptoms associated with the antihypertensives. The composite includes prolonged hospitalization beyond the typical stay (>2 days for a vaginal delivery, >4 days for a cesarean delivery), unscheduled clinic visits, Labor and Delivery triage visits or a postpartum readmission. The primary outcome is binary; if a patient has at least one of the composite outcomes she is considered to have the primary outcome. The secondary outcomes will include time to sustained blood pressure control (hours from initiation of medication to no additional changes to regimen), need to add additional antihypertensives (yes/no), clinically significant episodes of hyper- or hypotension (yes/no), creatinine levels at one week after discharge and six weeks postpartum, continued need for antihypertensives one week after discharge and six weeks postpartum (yes/no), side effects (listed), adverse events (listed), patient reported compliance (yes/no) and a patient satisfaction survey administered on the day of discharge from the delivery admission. The appointments at one week after discharge and six weeks postpartum are standard practice.

We plan to analyze this trial on an intention-to-treat basis. The primary outcome will be measured as the proportion of patients within each group that had at least one of the composite outcomes. To determine the baseline rate of our primary outcome, we looked at a small sample of randomly selected patients with postpartum hypertension who were discharged home on antihypertensives and observed the primary outcome occurs 70% of the time in this cohort. We believe that a clinically relevant decrease in this outcome would be to decrease this proportion below 50%. Therefore, we have chosen 40% as our target for what we would consider a successful intervention. For sample size, we are assuming an alpha of 0.05 and a power of 80%. Using a two-sided T-test in R comparing proportions of the two outcomes, we determined we will need 40 participants in each arm. Accounting for possible lack of follow-up, we will aim to enroll 45 in each arm, for a total of 90 patients.

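### The blood pressure control outcome contains no blood pressure value: it times the last regimen change by an unblinded provider, so a woman left above the protocol's goal with no change would score 0 hours

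*SAP*

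**What the plan says.** The SAP (Biostatistical analysis, secondary outcomes) includes "time to sustained blood pressure control (hours from initiation of medication to no additional changes to regimen"). The protocol (Research Design and Methods, study procedures) states the purpose of treatment in figures. Its target is that "systolic blood pressure is consistently less than 150 mmHg and diastolic blood pressure is consistently less than 95 mmHg", and the assigned drug is to be titrated to it. Labetalol is to be added if that goal is not met at a stated dose, or if "the patient’s provider believes the assigned agent (nifedipine or enalapril) is ineffective". The same section schedules clinic follow-up at one week after discharge and at "six weeks for blood pressure checks and to have basic metabolic panels drawn", and says elsewhere that vital signs will be monitored.

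One other SAP outcome concerns pressure: "clinically significant episodes of hyper- or hypotension (yes/no"). No threshold is attached to it. No outcome in either document is scored against 150/95.

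Two design features bear on the point. On blinding: "This is an open-label randomized controlled trial". On removal: "We would remove a patient from the study if she has an adverse reaction to any of the antihypertensives such as significant hypotension, uncontrollable hypertension". Not tolerating the drug is a further listed reason. Neither document says how the time outcome is scored for a woman whose regimen stops changing while she is above goal, or for a woman who is removed.

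**The concern.** The outcome is named for control of blood pressure, but what it records is prescribing. A regimen stops changing either because pressures are at goal or because nobody acted on pressures that were not. The definition treats these two situations alike, and the person whose action or inaction determines the score knows the assigned drug.

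The hypothesis is that women given enalapril will use fewer resources. If that is what the trial finds, a reader will ask at once whether pressures were equally well controlled in the two arms. Need for an added drug and continued need for treatment are also prescribing decisions, and the episode outcome has no cut-off. As planned, the outcomes give only a partial answer.

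**Working it through.** **The plan's own figure.** The SAP gives no figure for this outcome. Its one computed figure is the primary sample size, checked here only to show that it is separate. At 70% versus 40%, two-sided alpha 0.05 and 80% power, with unpooled variance:

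n = (1.960 + 0.842)² × (0.7×0.3 + 0.4×0.6) / 0.3² = 7.849 × 0.45 / 0.09 = 39.2, rounded up to 40 per arm.

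The stated 40 reproduces. Nothing below changes it.

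**Scoring check.** Three constructed women (assumed readings, not trial data), each starting at 158/98, are scored two ways:
- SAP rule: hours from first dose to last regimen change, 0 if there is none.
- Goal rule: hours from first dose to the first of an unbroken run of readings below 150 and below 95, with no later upward change.

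| Woman | Regimen changes | Readings | SAP rule | Goal rule |
|---|---|---|---|---|
| A | none | never at goal (156/97 at 72 h) | 0 h | not controlled |
| B | 12 h and 24 h | at goal from 36 h (142/88) | 24 h | 36 h |
| C | none | at goal from 12 h (146/92) | 0 h | 12 h |

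The SAP rule orders them A = C, then B. The goal rule orders them C, then B, then A. The woman who was never controlled moves from joint best to worst. This result needs no assumption about frequency. It follows from a definition with no pressure in it.

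**Precision of a comparison at goal.** The documents give no at-goal rate, so a range is assumed, equal in both arms. The half-width of the 95% CI for the difference is 1.96 × √(2p(1−p)/n):

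| Assumed p | n = 40 per arm | n = 45 per arm |
|---|---|---|
| 90% | 1.96 × √(0.18/40) = 13.1 points | 1.96 × √(0.18/45) = 12.4 points |
| 80% | 1.96 × √(0.32/40) = 17.5 points | 1.96 × √(0.32/45) = 16.5 points |
| 50% | 1.96 × √(0.50/40) = 21.9 points | 1.96 × √(0.50/45) = 20.7 points |

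Such a comparison would be descriptive. It could show a large imbalance in control but could not exclude a moderate one.

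**The case against.** The strongest reply is that the definition is not detached from the goal. Providers are told to titrate to 150/95 and to add a second drug if that fails. If they comply, changes stop when the goal is met and the last change is a reasonable marker of control. Woman A arises only when a provider does not act as instructed, and nothing in the documents says how often that would happen or that it would differ by arm. This stands, and it limits the point to a weakness in a proxy. It does not remove the weakness, because nothing planned checks the proxy against readings.

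Second, the 0 hours is an inference. The SAP gives no rule for a woman with no change, and an analyst could rely on the outcome's name to exclude one who was never controlled. That is possible, but the operational definition in parentheses does not say so.

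Third, a reader might infer that the trial will have no information on under-treatment. The documents do not support that. The episode outcome should pick up the more marked cases, and uncontrollable hypertension is among the events sent for safety review. What is missing is a threshold and any measure of attainment of goal.

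Fourth, a reader might infer that the primary composite is itself mostly a matter of provider choice. The documents do not say who initiates unscheduled clinic visits or triage visits, so that cannot be asserted.

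**Conclusion.** The point holds as a defect of definition in one secondary outcome. Followed literally, it gives a woman left above goal with no change the best possible score. That score is a tie with immediate success, not a unique first place. It is also ahead of a woman who was titrated to goal. Because no other outcome measures attainment of the goal, less resource use in one arm could not be readily separated from less active treatment.

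A reader might go further and infer that a result favouring one arm on this outcome would be the reverse of the truth. The documents do not support that. It would require under-titration that was both common and unequal between arms, and its frequency cannot be estimated from what is given. No size of bias is therefore claimed. The primary outcome, its analysis and the sample size are unaffected.

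**What to change.** 1. **Redefine the outcome in the SAP.** Count a woman as controlled only when charted readings meet the goal already in the protocol and no upward regimen change follows. State what counts as consistently below goal (number of readings or length of time). Restrict the analysis in hours to the delivery admission, where readings can be expected to be frequent; the two later checks cannot resolve hours. Women not at goal by discharge, or removed for uncontrollable hypertension, stay in the denominator as not controlled. They should be neither scored 0 hours nor treated as non-informatively censored.
2. **Keep the existing measure under its own name.** Report time to last regimen change separately, labelled as such.
3. **Add the proportion at goal.** At the one-week and six-week checks already scheduled, report by randomised arm the number with a reading, the proportion below the protocol's goal, and the difference with a 95% CI. Label it a descriptive secondary outcome and place it beside the primary result.

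The cost is SAP wording, some extra chart extraction and one more unpowered secondary outcome. No visit, procedure or treatment rule changes. The revision should be made before outcomes are compared by arm.

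### The SAP lists hypertensive and hypotensive episodes as one yes/no secondary item, which carries no direction and can dilute or, in some cases, hide a difference between the arms

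*SAP*

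**What the plan says.** The SAP's only section, Biostatistical analysis, lists the secondary outcomes in one sentence. One entry is "clinically significant episodes of hyper- or hypotension (yes/no"). It gives no threshold for clinical significance in either direction and does not say whether the two kinds of episode are recorded or compared separately. No test is named for any secondary outcome.

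Three neighbouring entries in the same list bear on blood pressure:
- time to sustained control ("The secondary outcomes will include time to sustained blood pressure control");
- "need to add additional antihypertensives (yes/no");
- "side effects (listed), adverse events (listed").

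The protocol (Research Design and Methods) describes an open-label trial in which the dose of the assigned drug is adjusted toward a goal: "systolic blood pressure is consistently less than 150 mmHg and diastolic blood pressure is consistently less than 95 mmHg". In the same section, the reasons for removing a woman from the study name the two directions separately: "such as significant hypotension, uncontrollable hypertension or intolerance of the medication". Under Data and Safety Monitoring, uncontrollable hypertension is one of the adverse events to be reviewed; hypotension is not named there. Neither document splits the SAP item.

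**The concern.** Both drugs are adjusted toward a blood-pressure goal, and a woman can miss that goal in two ways. A hypertensive episode suggests too little effect and a hypotensive one too much. If a woman scores yes for either, the score has no direction.

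This is unlike the primary composite, where every component means more use of medical resources. Here a higher pooled rate in one arm could mean under-treatment, over-treatment or both. Similar pooled rates could mean that the drugs behave alike, or that one has more hypertensive and the other more hypotensive episodes.

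The gap is greatest for hypotension. The add-on outcome partly marks under-treatment, because the protocol ties adding labetalol to missing the goal at a stated dose or to the provider judging the assigned drug ineffective. Hypotension has no outcome of its own with a planned comparison. It could appear among the listed side effects or adverse events, but no comparison by arm is specified for those.

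**Working it through.** **Inputs from the documents.** SAP: 45 enrolled per arm, 40 needed per arm, alpha 0.05, two-sided comparison of proportions. No rate, threshold or power is given for hypertensive or hypotensive episodes.

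**The plan's own figure.** The SAP's 40 per arm is for the primary outcome, 70% against 40% at 80% power. The unpooled normal formula gives

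n = (1.960 + 0.842)² × (0.70×0.30 + 0.40×0.60) / 0.30² = 7.85 × 0.45 / 0.09 = 39.2, so 40.

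Allowing for 10% loss, 40 / 0.90 = 44.4, so 45. The sample size reproduces and is not in question. It serves here only to fix n.

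**Pooled rate.** If h and l are the proportions with at least one hypertensive and at least one hypotensive episode, and the two are independent within a woman, the proportion with either is 1 − (1 − h)(1 − l).

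- 30% and 5%: 1 − 0.70×0.95 = 33.5%. 10% and 25%: 1 − 0.90×0.75 = 32.5%.
- 40% and 5%: 1 − 0.60×0.95 = 43.0%. 20% and 15%: 1 − 0.80×0.85 = 32.0%.
- 30% and 2%: 1 − 0.70×0.98 = 31.4%. 10% and 8%: 1 − 0.90×0.92 = 17.2%. 10% and 5%: 1 − 0.90×0.95 = 14.5%.
- 20% and 5%: 1 − 0.80×0.95 = 24.0%.

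**Power.** Exact enumeration of two binomial samples of 45, with the two-sided pooled-variance z-test at 0.05. All episode rates are assumptions.

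| Arm A hyper/hypo | Arm B hyper/hypo | Pooled rates | Power pooled | Power, hyper alone | Power, hypo alone |
|---|---|---|---|---|---|
| 30% / 5% | 10% / 25% | 33.5% v 32.5% | 5% | 69% | 81% |
| 40% / 5% | 20% / 15% | 43.0% v 32.0% | 19% | 56% | 39% |
| 30% / 2% | 10% / 8% | 31.4% v 17.2% | 36% | 69% | 26% |
| 30% / 2% | 10% / 5% | 31.4% v 14.5% | 50% | 69% | 9% |
| 40% / 5% | 20% / 5% | 43.0% v 24.0% | 50% | 56% | no true difference |

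**Sensitivity, first row.** If no woman has both events, the pooled rates are 30 + 5 = 35% and 10 + 25 = 35%, and pooled power is again about 5%. With 40 per arm, pooled power is about 5%, against 63% and 76% apart. The pattern does not depend on independence or on the allowance for loss.

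**Reading the table.** In the first row, differences of 20 points in each direction leave a pooled difference of 1 point, and the test rejects about as often as its false-positive rate. In the middle rows the offset is partial: the pooled difference stays visible (11 to 17 points) but power falls. In the last row there is no offset, and separating the outcomes costs no power for hypertension.

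**The case against.** **The wording may not mean one variable.** The same sentence puts a single yes/no tag on continued need for antihypertensives at two time points, which are plainly two variables. This stands in part: the tag alone does not prove pooling. Two events joined by one conjunction under one tag still read most naturally as one variable, and nothing elsewhere says otherwise. If the investigators intend two, the same edit settles it.

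**A reader might infer that the two harms will cancel out, or that opposite imbalances are the likeliest difference.** The documents support neither. They give no episode rates and do not say that either drug is more potent, and titrating both arms to one goal could equally narrow differences in both directions. Near-complete cancellation needs opposite differences of similar size. If hypotension is uncommon, the effect is dilution. Pooling can even help if one drug has fewer of both events.

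**A reader might infer that this is the only planned comparison bearing on blood-pressure risk.** It is not. Add-on antihypertensives and time to sustained control are separate secondary outcomes, and the first partly marks under-treatment. What remains is the narrower gap for hypotension.

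**It is a minor item.** It is one of several secondary outcomes with no stated test or decision rule, and two rows could be shown at reporting if direction was captured. That is true, but the plan does not say that direction will be captured.

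**The undefined term in an open-label trial** is a separate definition problem, not evidence of masking. It is best settled in the same edit.

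**Conclusion.** The point holds in a limited form. Read naturally, the item pools two opposite failures of blood-pressure control that the protocol itself names separately. The pooled variable has no direction, and what it loses ranges from a little to nearly everything: in the cases shown, pooled power is 5% to 50%, where hypertension alone would have 56% to 69%. These figures rest on assumed rates, 45 women per arm, a two-sided 0.05 test and independent events; they show the range and do not predict the trial.

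It would be too strong to say that the plan will report equal safety when the drugs differ. The SAP calls this a secondary outcome, not a safety outcome, and makes no claim of equal safety. Neither the primary outcome nor the sample size is affected. The item should be changed because the better form is cheap and the pooled form is hard to interpret whichever way it comes out.

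**What to change.** Replace the item in the SAP with two secondary outcomes, each yes/no:

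1. at least one hypertensive episode;
2. at least one hypotensive episode.

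Count both from randomisation to the six-week visit in all randomised women, in keeping with the intention-to-treat analysis. A window opening at the first dose would leave out women randomised but never dosed. State that an episode leading to removal from the study counts as an event.

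The investigators should fix a definition for each outcome before any data are viewed by arm. It should name the sources (inpatient readings, clinic visits, unscheduled encounters) and say how a symptomatic episode without a captured reading is handled. The protocol's titration goal is not an episode definition and need not serve as one. These are outcome definitions only and change no treatment rule.

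Report each outcome by arm with a risk difference and 95% CI. Any combined outcome should be labelled supplementary.

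The cost is a few lines of SAP text, a data field that records direction, and one more row in the table. The protocol already provides for monitoring of vital signs and for blood-pressure checks at both follow-up visits. The downside is one more secondary comparison, with limited power for hypotension if it is rare (9% for 2% against 5%), so the interval should carry the interpretation. The sample size does not change.
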